### ***Gait Assessment***

- During the locomotion tests only, inertial measurement units (IMUs) will be attached to the shoes, waist and one or both arms of the subject, using soft straps with Velcro closures. The IMUs to be used may be wired or wireless; if wired, the cables will be restrained inside clothing or with straps. The sensors will log acceleration, angular velocity, magnetic field, and altitude data while the subject walks in the hallway (6MWT) or on a short circuit starting from a seated position (TUG) or a standing position (SSWS, FCWS). Data from these sensors will be used to assess stride length, speed, foot placement variability, symmetry, and gait stability.

### ***Functional MRI scans:***

- Participants who will undergo an MRI scan will be screened for MRI eligibility using the UW Department of Radiology's standard clinical MRI screening form.
- All patients in the study will be scanned at two time points (before and after intervention).
- Healthy Normals in the Typical Comparison group will be scanned once.
- Healthy Normals in the Pilot group will not be scanned.

### ***Training on the robotic rehabilitation cycle:***

- Patients assigned to the "robotic" and "control" groups will receive training following the procedure outlined below; these patients will complete 12 training sessions over one month.
- Healthy normal subjects will receive modified training on the device up to five (5) times.

## **Robotic Training Group (Robotic Group): Procedure**

### ***Robotic therapy protocol description:***

The "Robotic" group will be trained using a robotic training protocol, designed to incentivize recovery of volitional motor control by dynamically changing task demands throughout the training period. One or more target tasks will be chosen to incentivize motor activity mimicking different sub-functions of gait, including some which are not normally excited in typical cycling behavior. Candidate tasks include: leg swing-through (hip flexion with knee extension near the most proximal pedal position); leg retraction (hip extension with knee flexion near the distal pedal position); leg extension (hip and knee extension – the power stroke of normal pedaling); leg retraction (hip and knee

flexion –the passive recovery stroke in normal pedaling); step-like loading (hip and knee extension while bike pedals backward through proximal pedal position, then hip and knee flexion through the distal position); and a “foot placement-like” task (alternating medial and lateral force) during normal pedaling. Also, tasks may be designed to target non-gait motions such as hip ab/adduction. The required task may be changed periodically, to incentivize attention to task and cortical control, rather than short-term adaptation (e.g. cerebellar).

A user display screen will indicate the desired task at all times, and indicate measures of asymmetry and performance. Performance will be defined as “task matching performance,” computed as the normalized projection of the vector-valued foot force or EMG signal (all channels) onto the specified task vector. Using this metric, 1.0 indicates perfect task matching; zero (0.0) indicates no force/EMG signal in the direction of the specified task; negative values indicate force production opposed to the specified task (impossible for EMG), and values greater than 1.0 indicate excess force or EMG activity in the specified pattern. We will also explore other methods for reducing multidimensional data to informative summary measures. Performance will be displayed to the user on a computer screen using a “speedometer” or similar graphical display, and will be incorporated into the control system of the robotic cycle and recorded for later analysis. Alternative measures of performance may also be used.

The controller will reward good performance with increased crank speed, and will penalize errant coordination with decreased crank speed. The subject’s explicit goal will be to maintain a constant speed; this will only be achievable through proper motor control. Errors in either direction (too high/too low) will result in a crank speed error, representing imperfect performance. As subjects gain skill in the task, task difficulty will be increased by increasing the target signal magnitude of the specified task. This specific task is one among many possible therapy designs, which this Pilot study is intended, in part, to choose among. The specific reward structure and task definitions may be modified based on tests with healthy controls as well as early patients, in order to optimize the therapy delivered. All forms of task will involve only seated pedaling motions. Possible other tasks include (but are not limited to): pedaling that emulates a typical bike or exercise bike; tasks that change resistance torque instead of crank speed as a reward; tasks that reward forces opposing the motion of the pedals; and tasks that use a variety of different calculations to determine the “task matching performance” metric.

This therapy protocol will occupy 30 minutes of each training session. Prior to testing, EMG electrodes will be placed on the major muscles of both legs, a procedure that takes roughly 15 minutes. Another 15 minutes is allotted for changing clothes, briefing

and debriefing the subject, and other ancillary study activities. The total time allotted per training session is 1 hour.

***fMRI Scanning Protocol description:***

fMRI scans will be used to measure task-specific cortical activity in sensorimotor areas as outlined in the *data processing* section. Due to uncertainty about available testing equipment, one of two protocols may be used for fMRI testing: physical stepping with an MRI-compatible stepping machine (Ergospect GmbH; Forouzan et al., 2014), available at UW-Madison through [name]; or imagined/visualized cycling. The preferred activity is actual stepping with a passive MRI- compatible stepper. Imagined/visualized cycling is proposed as a suitable substitute activity within the constraints of the fMRI environment if for some reason the stepping machines cannot be used.

If the MRI-compatible equipment is available for this study, each subject will recline and position his head within the MRI bore, while his feet are clipped to the pedals. The torso will be stabilized with straps to minimize motion artifacts affecting the scan. During the scan, the subject will be instructed to step at a constant speed, while fMRI scans incrementally identify the activity in different portions of the brain. This protocol will best match the context of the fMRI scan to that of the training task.

If the MRI-compatible equipment is determined to be unsuitable for this study, each subject will recline and position his head within the MRI bore, with the body relaxed and stationary. During scanning, the subject will be instructed to imagine consistently performing the cycling task used in training. While not strictly equivalent to the real task, an imagined task (motor imagery) has been shown to evoke neural activity much as real tasks do (Pfurtscheller and Neuper, 1997; Porro et al., 1996; Sharma et al., 2006). Changes in such activity during imagined tasks will suggest that neural reorganization occurred.

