### ***Secondary objective***

To examine plasticity changes as measured by fMRI measures before and after robotic pedaling therapy, in comparison to an aerobic pedaling task.

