## **Research Design and Methods**

Forty (40) adult stroke patients as well as 80 healthy controls will be enrolled in this study. The 40 stroke patients will be subdivided into two equal groups; the “robotic” group will receive the targeted training task, while the “control” group will perform duration-matched aerobic pedaling. 20 healthy controls enrolled (age 50-85) will contribute to a normative data set. They will receive up to 5 training sessions in a modified robotic paradigm and up to 1 fMRI scan. The other healthy control subjects (age 18-50) will participate as pilot subjects during early phases while the device and therapeutic task specifications are developed, and throughout the project while the device and tasks are refined. These pilot subjects will test the robotic device; help us determine how subjects are able to control muscle activity and foot endpoint force, independent of neurological injury; and/or test the fMRI scanning protocol and exercises. Because these subjects are contributing to development, we have no a priori expectation of how many will be needed. We guess roughly 20, but we plan to recruit as many as ongoing development needs require (up to 60).

Several studies have shown that recovery of functional and motor capabilities after a stroke is a long process that occurs over several months and even years following a stroke (Takahashi et al., 2005; Ward et al., 2003). Similarly, age is a significant factor that influences recovery. The current protocol is aimed at developing a rehabilitation device and protocol that has the potential to facilitate recovery in patients with lower-limb motor impairments. This is a Pilot study and the results of this study should help us to identify the patients and level of impairment for which this intervention is most optimal. The long-term goal is to apply this therapy to patients at all stages of recovery from stroke. However, we initially restrict ourselves to a subset of patients based on time since stroke onset, to reduce likely statistical scatter in the results. Each patient will serve as their own control in this repeated-measures design (evaluations pre-intervention and post-intervention).

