***fMRI data:***

SPM5 (Wellcome Department of Cognitive Neurology, London, UK) will be employed for motion correction and used to normalize the EPI BOLD images to a standard space using a 12 parameter linear transformation. The images will be then spatially smoothed using an 8.0 mm Gaussian kernel. Finally, the statistical package contained within SPM5 will be used to estimate the effects of condition at each voxel according to the general linear model. The analysis will be entered into SPM5 as an epoch design of the fixed response/box car form convolved with canonical HRF, reflecting the appropriate activation and rest periods within the total scanning period. Images will be high-pass filtered at 128 s to remove low- frequency drifts in blood oxygen level-dependent signal.

Percent signal change (after vs. before) will be compared statistically between the two groups using unpaired two-sample t-tests between the robotic and aerobic groups. A repeated measures ANOVA will be performed with the dependent variable being the percent signal change and between subjects factor Group (robotic therapy, aerobic therapy), and within subject factor Time (before and after training).

Along with percent signal change over time, we will also compute region-wise laterality index. ROIs will be predefined in each hemisphere. For each ROI, laterality index (LI) will be defined as: Number of activated voxels in the affected hemisphere / [voxels in the left hemisphere + voxels in the right], thus giving LI for each ROI. LI = 0.5 indicates symmetrical activation; LI < 0.5 indicates an activation deficit on the affected side, and LI > 0.5 indicates increased activation of the affected side. This index will provide a way of

understanding the contribution of each brain area (ROI) to the overall task-related activation in one session and changes in laterality over time. The percent signal change and LI are purely quantitative measures, in order to ensure that change in plasticity over time is captured adequately and does not rely on individual fMRI reader's abilities to gauge these changes simply on the basis of a "visual read" of the fMRI scans.

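### If the stepping scan is used, step rate and load are neither matched between the two scans nor recorded, so a change in activation may partly reflect motor output rather than plasticity.

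*Combined protocol and SAP*

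**What the plan says.** The secondary objective is "To examine plasticity changes as measured by fMRI measures before and after robotic pedaling therapy, in comparison to an aerobic pedaling task". Each patient is scanned twice, before and after the intervention.

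The section fMRI Scanning Protocol description allows two scan tasks. The first choice is physical: "The preferred activity is actual stepping with a passive MRI- compatible stepper". The only instruction about how to perform it is this: "During the scan, the subject will be instructed to step at a constant speed, while fMRI scans incrementally identify the activity in different portions of" […]. If the stepper proves unsuitable, "the subject will be instructed to imagine consistently performing the cycling task used in training", with the body at rest.

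Under Data Processing/Data Analysis, the fMRI data section models each scan with activation and rest blocks. It then states: "Percent signal change (after vs. before) will be compared statistically between the two groups using unpaired two-sample t-tests" between the robotic and aerobic groups, followed by a repeated measures ANOVA with Group and Time, and a laterality index built from counts of activated voxels. The Behavioral Data section adds a multivariate ANOVA that also asks whether the measures change over time, and a regression of behavioral scores on percent signal change and on tracking error in the last training session.

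On piloting, Research Design and Methods says pilot subjects may, among other things, "and/or test the fMRI scanning protocol and exercises", while the section Functional MRI scans says: "Healthy Normals in the Pilot group will not be scanned".

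**The concern.** Activation during a movement task can depend on how much movement is made. On a passive stepper the patient supplies the rate and the effort. If a patient steps faster or harder at the second scan than at the first, percent signal change can differ between scans with no reorganization of the brain.

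Two features make this more than a missing detail. First, the plan reads the change as plasticity, so the alternative explanation bears on the conclusion itself. Second, nothing measured in the scanner would show afterwards whether stepping had changed, so the problem could be neither diagnosed nor described once the scans are done.

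**Working it through.** No figure in the plan is in dispute. The check has three parts.

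**1. Is stepping controlled or measured anywhere?**

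- *Instruction* (fMRI Scanning Protocol description): constant speed during a scan. There is no value, pacing cue, range or resistance, and no requirement that the second scan repeat the first.
- *Device* (same section): passive. No motor is described that would set rate or load.
- *EMG and leg strength* (Subject Assessments, items 9 and 10): taken on the rehabilitation cycle, not in the scanner.
- *Inertial sensors* (Gait Assessment): worn for the walking tests only.
- *First-level fMRI model* (fMRI data): activation and rest blocks, with no step-rate or force regressor.
- *Group tests* (fMRI data): no performance covariate.
- *Tracking error* (Behavioral Data): comes from the last training session and predicts behavioral scores. It does not adjust the fMRI change.
- *15 to 50 rev/min* (Aerobic Training Group procedure): a training speed for one arm, not a scanner speed.

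So rate and load are not set, matched or recorded.

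**2. Which analyses does this reach?** Write a patient's change in percent signal change as p + s, where p is the plasticity part and s the part due to a change in stepping. Subscripts R and A denote the robotic and aerobic arms.

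- *Time effect:* the mean change is mean(p) + mean(s). Nothing removes mean(s), so this is directly exposed.
- *Regression of behavioral scores on signal change:* if patients who walk faster also step faster in the scanner, s correlates with the score even when p = 0. This is directly exposed.
- *Between-arm comparison:* the contrast is (p_R − p_A) + (s_R − s_A). A stepping change common to both arms cancels. Bias remains only if s_R differs from s_A.
- *Laterality index:* with A activated voxels on the affected side and U on the other, LI = A/(A + U). If both counts scale by k, LI = kA/(kA + kU) = A/(A + U), unchanged. It moves mainly when the change is asymmetric.

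Is s_R ≠ s_A plausible? In the robotic arm, the section Robotic therapy protocol description has patients hold crank speed through their own motor control, with the target magnitude raised as skill improves. In the aerobic arm, a motor adds assistance or resistance to make up for the patient's performance. One arm thus rehearses self-controlled speed and the other has speed largely held for it. That makes a difference on a passive stepper plausible; it does not establish one.

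**3. How much could it matter? Illustration only.** The documents give no link between stepping and signal, and no SD for the signal change. Assume no true plasticity, a two-sided 0.05 test, n = 16 (the evaluable number per arm in Sample Size), and a stepping shift of b SD of the change score. Rejection rates come from the noncentral t distribution:

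- between arms: noncentrality b√(n/2) = b√8, df = 2 × 16 − 2 = 30
- within one arm, pre to post: noncentrality b√n = 4b, df = 16 − 1 = 15

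| Assumed b (SD) | Between-arm test rejects | Within-arm test rejects |
|---|---|---|
| 0 | 5% | 5% |
| 0.2 | 8.5% | 12% |
| 0.3 | 13% | 20% |
| 0.5 | 28% | 47% |
| 0.8 | 59% | 85% |

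In the between-arm column, b is the *difference* in shift between arms. In the within-arm column, it is the shift in that arm. The values of b are assumptions, not estimates.

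**The case against.** The strongest reply is that the control arm already handles this. The comparison is randomized against duration-matched pedaling, and a stepping change shared by both arms drops out. That is right for the between-arm contrast. It does not protect the Time effect or the regression, both of which the plan also interprets.

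A second reply is that constant speed may have been meant to apply across scans. The text does not say so, gives no value, and leaves the rate to the patient.

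A third is that training does not aim at faster movement. This stands. A reader might infer that patients are trained to move faster and push harder, so that activation must rise. But robotic patients aim at a steady crank speed, with error in either direction counted against them, and the aerobic arm uses constant-velocity control. The target magnitude does rise in the robotic arm, but the protocol presents that task as one of several possible designs. The direction of any stepping change is therefore open.

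A reader might also turn the walking gains expected in Sample Size (0.18 to 0.21 m/s) into a percentage rise in activation. The documents do not support that: those are overground speeds from a cited locomotor study, and nothing links them to reclined stepping or to signal.

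Finally, under imagined cycling there is no step rate or load to match, so the point does not apply in this form.

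**Conclusion.** The point holds for the stepping protocol. As written, percent signal change may partly reflect a change in stepping rate or effort. The Time effect and the regression are directly exposed, the between-arm comparison only through a differential change, and the laterality index mainly through an asymmetric one.

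A reader might go further and conclude that the design cannot support the secondary objective at all. That is too strong: the randomized contrast is valid unless stepping changes differ between arms, and the documents make such a difference plausible without showing it.

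The size of the bias cannot be computed from the documents, and the rejection rates above rest entirely on assumed shifts. The outcome is secondary and the study is a pilot, so this is a change that should be made rather than one on which the trial depends. It is worth making because it is cheap and cannot be repaired after the scans.

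**What to change.** **fMRI Scanning Protocol description.** For the stepping task, set each patient's step rate and device setting at the first scan and cue the rate with a visual or auditory pacer. Use the same settings at the second scan. Log the step count in every active epoch at both scans.

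**fMRI data.** Report in-scanner step rate by arm and time point, so that readers can see whether stepping was matched. Label any analysis adjusted for the change in step rate as exploratory: that change arises after randomization and may itself be part of recovery, so adjusting for it may remove a real effect. Matching the task by design is the main remedy.

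**Piloting, separately.** Reconcile Research Design and Methods, where pilot subjects may test the scan protocol, with Functional MRI scans, where they are not scanned. This is a documentation conflict, not proof that the task cannot be tried out, since the matched controls each have one scan.

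**Cost.** A pacing cue, a step log and a short descriptive table. The paced scan will no longer show a change in preferred stepping speed, but preferred walking speed is already captured by the gait tests.

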### ***Secondary outcomes***

The change in strength of brain activity in affected regions of interest (ROI) within the brain, and the change in laterality index (LI) comparing the same ROI in affected and unaffected hemispheres. Regions of interest include the primary sensorimotor cortex, the supplementary motor area, and the cerebellum.

Normative data on the progression of motor learning (behavioral measures) and brain activity (fMRI) in control subjects of similar age to the stroke-prone population (50-85 years).

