### **Healthy Normal Controls**

#### **Non-Stroke Group 1 (Typical Comparison Group): Procedure**

Healthy Normal subjects in this group will be administered the same behavioral measures as the Stroke groups, and 1 fMRI scan while stepping (or imagining stepping) at the beginning of the study. Subjects will then undergo up to 5 training sessions on the robotic cycle with a modified training task. This task will incentivize performance of a novel motor task, such as eccentric force control, mediolateral force control, or EMG coordination in a pattern different from normal cycling. Performance in matching the target task will be evaluated across the training sessions.

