### ***Data from Healthy Normals:***

The EMG data from healthy normals will help us to determine if the subjects are able to learn novel motor tasks that decompose traditionally synergistic muscle groups during cycling, and whether they show any handedness bias. The fMRI data from normals will show traditional areas of activation while performing or imagining a motor task; the average map derived from these subjects will serve as a control for the patients.

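### If the MRI stepper is not used, the scanning protocol has subjects imagine cycling, but the healthy reference group is to imagine stepping

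*Combined protocol and SAP*

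**What the plan says.** The section fMRI Scanning Protocol description allows two scan activities because it is uncertain which equipment will be available. Physical stepping on an MRI-compatible device is preferred. If it cannot be used, "Imagined/visualized cycling is proposed as a suitable substitute activity within the constraints of the fMRI environment", and the instruction is that "the subject will be instructed to imagine consistently performing the cycling task used in training". This section sits under the Robotic group's procedure. The Aerobic group's section says its protocol is identical apart from the exercise.

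The healthy comparison group has its own section, Non-Stroke Group 1 (Typical Comparison Group): Procedure. It provides for "1 fMRI scan while stepping (or imagining stepping) at the beginning of the study", followed by up to five sessions on a modified task. Of that task it says: "This task will incentivize performance of a novel motor task, such as eccentric force control, mediolateral force control".

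Two sections give this group's scan a purpose. Under Data from Healthy Normals, "the average map derived from these subjects will serve as a control for the patients". Under Secondary outcomes, the plan lists "Normative data on the progression of motor learning (behavioral measures) and brain activity (fMRI) in control subjects of similar age". The section Functional MRI scans schedules two scans for each patient and one for each healthy subject in this group.

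**The concern.** A reference map is useful only if it was acquired under the same task as the scans it is set against. In the imagery fallback, one section names cycling and another names stepping, and no passage reconciles them. A study team following both sections to the letter would build the healthy map from imagined stepping and compare it with patients who imagined cycling. A region that looked different in patients could then reflect stroke or simply the different imagined movement, and the data could not say which. The conflict has to be settled before scanning starts, because a completed scan cannot be given a different task afterwards.

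There is also a smaller gap. The scanning section refers to the task used in training without saying whether the two arms, which train differently, imagine one common task. Nor does it say that a patient imagines the same thing at both scans.

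**Working it through.** No sample-size or power figure bears on this point, so the check is mainly a comparison of the text.

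**1. The scan task under each option**

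| Option | Patients | Healthy comparison group | Same task? |
|---|---|---|---|
| Physical stepper (preferred) | stepping | stepping | yes |
| Imagery, each section as written | imagined cycling, as in training | imagined stepping | no |
| Imagery, scanning section's instruction applied to the healthy group too | imagined cycling, as in training | its own modified novel task | no, and this contradicts the group's own section |

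The last row matters because the scanning section speaks of each subject, which might be taken to cover healthy subjects. That reading does not repair the conflict, because the healthy group's training task is not the patients' training task.

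**2. Does another section settle it?** The Project Summary speaks only of simple motor tasks performed or imagined, and Data from Healthy Normals only of a motor task. Neither chooses between cycling and stepping.

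**3. Can the analysis separate task from group?** Write m(group, task) for mean activation in a region. What would be observed is

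m(patient, cycling) − m(healthy, stepping) = [m(patient, cycling) − m(healthy, cycling)] + [m(healthy, cycling) − m(healthy, stepping)].

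The first bracket is the patient-control difference of interest. The second is a pure task difference. No healthy subject would imagine cycling and each is scanned once, so the second bracket is never observed and cannot be subtracted.

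**4. How many scans are involved?**
- Healthy: up to 20 × 1 = 20.
- Patients: 40 × 2 = 80 planned.
- With the 20% dropout assumed under Sample Size, 20 × 0.80 = 16 complete per arm, giving 2 × 16 × 2 = 64 scans from completers.

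All 20 healthy scans would be on a different imagined task from all the patient scans.

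**5. The patients' own change scores.** If a patient imagines task A before training and task B after it, the observed change is the training effect plus the difference between B and A. That extra term is zero when A and B are the same. The section fMRI data analyses this before-after change, and the scanning section takes changes during imagery to suggest neural reorganization. That interpretation needs a constant task. The plan does not state one: the robotic target task may change periodically during training, and the Timeline lists the baseline scan before the first training session.

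**The case against.** The strongest reply is that this is loose drafting. The only detailed scan description names one imagery activity, cycling, and the word stepping in the healthy group's section may just echo the physical option beside it. That may well be the history. It does not remove the conflict, since the two sections still give different instructions and nothing in the plan says which governs.

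A second reply is that the plan specifies no statistical test of patients against healthy controls. The analysis sections cover patients before and after training and robotic against aerobic therapy. This is correct, and it limits the claim: a reader might infer an inflated false-positive rate in a patient-control test, but the documents neither state such a test nor give a figure for the task difference. What stands is that the healthy map is assigned the role of a control for the patients, and as written it could not serve that role cleanly.

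A reader might also infer that the two arms imagine different tasks, so that the between-arm fMRI comparison is biased. The documents do not support that. No passage assigns arm-specific imagery. The fallback is named generically as imagined or visualized cycling, the plan says "All forms of task will involve only seated pedaling motions", and the aerobic arm's protocol is otherwise identical. The statement that "The specific reward structure and task definitions may be modified based on tests with healthy controls as well as early patients" concerns development of the therapy; it does not show that one patient's imagined task changes between scans. Even under an arm-specific reading, an additive task difference that stayed constant over both scans would cancel in the change score. What remains is silence on the point, which calls for clarification and does not demonstrate bias.

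**Conclusion.** The plan is wrong as written: it contradicts itself on the imagined task. Under the fallback, the scanning section calls for imagined cycling and the healthy group's section for imagined stepping, while the healthy map is to be the patients' reference. All of the up to 20 reference scans would be affected. How far this would distort the map cannot be derived from the documents, which give nothing on how activation differs between the two imagined movements.

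The point is minor. It arises only if the stepper is not used, and it concerns secondary fMRI outcomes in a pilot study. Gait outcomes and the preferred stepping protocol are untouched. The conclusion rests on reading the healthy group's section literally and on the stated use of its map. The plan's silence about the two arms and the two scans is a secondary matter of clarity.

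**What to change.** In Non-Stroke Group 1 (Typical Comparison Group): Procedure, replace the imagined-stepping alternative with imagining the same cycling task that patients imagine under the scanning protocol. Describe it so that healthy subjects who have not trained on the cycle can follow it.

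As a secondary clarification, add to fMRI Scanning Protocol description a clause saying whether both arms imagine the same task, and a statement that each patient's imagined task is the same at both scans.

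The cost is wording in two sections and one written imagery instruction, with no added scans, visits or staff. Aligning the healthy group has no scientific downside. Choosing one generic task for both arms would give up part of the scanning section's aim of measuring task-specific activity, so the sponsor could instead keep arm-specific imagery and justify it. In that case a single healthy map could match only one arm's imagined task, and the plan should say which.
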